5.4.2.1.15. Flares

The incidence rate will be calculated and summarized for each type of on-treatment or off-treatment flares (virologic, biochemical and clinical) separately, as well as the overall incidence of participants experiencing at least one flare, regardless of type. Additionally, for each participant the total number of flares the participant experienced will be counted by type. Such counts will be used to summarize the distribution of the total number of flares by type.

For on-treatment biochemical flares, the incidence of flares causing treatment discontinuation will be summarized. Further, for off-treatment flares, the count and percentage of participants who experienced a flare followed by NA re-treatment will be summarized by flare type. Similarly, the incidence of flares followed by the achievement of HBsAg seroclearance (at any time) will be summarized by flare type.

Flares that are associated with signs of liver decompensation will be provided in a listing.

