1.2. Study Design

This is a Phase 2a, open-label, single-arm, multicenter study to assess efficacy, safety, tolerability and pharmacokinetics of treatment with JNJ-3989, JNJ-6379 (as applicable), NA, and PegIFN- α 2a in virologically suppressed patients with chronic hepatitis B virus infection. Prior to Protocol Amendment 3, the study intervention also included JNJ-6379. Note that as of Protocol Amendment 3, JNJ-6379 has been removed as study intervention and the study will continue with JNJ-3989, NA and PegIFN- α 2a only. Participants had to stop JNJ-6379 treatment immediately after the implementation of Urgent Safety Measure (USM) and approval of the protocol amendment 3.

Approximately 50 virologically suppressed CHB-infected participants, 18-65 years (inclusive) of age, will be enrolled in this study. Approximately 40% HBeAg-positive participants will be enrolled.

[figure not shown]
The study will be conducted in 4 periods:

- Screening period (4 weeks [if necessary, can be extended to a maximum of 8 weeks decided on a case-by-case basis and in agreement with the sponsor]).
- Treatment Period 1 (12 weeks) consisting of combination treatment with JNJ-3989 + NA.
- Treatment Period 2 (12 weeks) adding PegIFN- α 2a to the combination treatment regimen of Treatment Period 1.
- Follow-up (FU) Period (48 weeks).

The total duration of individual participation will be up to 76 weeks (including 4 weeks of screening).

A schematic of the trial prior to Protocol Amendment 3 is presented in [Figure 1](#).

Figure 1: Schematic Overview of the Study – Prior to Protocol Amendment 3

[figure not shown]

ALT: alanine aminotransferase; DNA: deoxyribonucleic acid; EOS: end of study; EOSI: end of study intervention; FU: follow-up; HBeAg: hepatitis B e antigen; HBsAg: hepatitis B surface antigen; HBV: hepatitis B virus; JNJ-3989: JNJ-73763989; JNJ-6379: JNJ-56136379; LLOQ: lower limit of quantification; n: number of participants; NA: nucleos(t)ide analog; PegIFN-α2a: pegylated interferon alpha-2a; ULN: upper limit of normal; Q4W: every 4 weeks; QD: once daily; QW: once weekly.

^a. If NA treatment completion criteria (HBsAg <10 IU/mL, and HBeAg-negative, and HBV DNA <LLOQ, and ALT <3x ULN) have been met at Week 24, NA will be stopped at the next scheduled visit (ie, FU Week 2), otherwise NA treatment will continue during the complete FU period.

A schematic of the trial as of Protocol Amendment 3 is presented in [Figure 2](#).

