4. POPULATIONS (ANALYSIS SETS) FOR ANALYSIS

Due to a potential impact of future Coronavirus Disease (COVID-19) pandemics on the study data collection, study treatment adherence and study conduct, the modified Full Analysis Set (mFAS) and modified IFN-FAS (mIFN-FAS) are defined to target the estimation of effects without the pandemic-related influences.

The primary set for the efficacy analyses will be the FAS set, and for the safety analyses the safety set. The IFN-FAS and modified FAS/IFN-FAS analysis sets will be used if there is a difference of at least 2 participants between analysis sets.

Table 2: Analysis Sets for Analysis

Analysis Sets	Description
Screened	All participants who signed the ICF for the Master Protocol and an ICF specific for the ISA.
Enrolled	All participants who were enrolled in this ISA.
Full Analysis Set (FAS)	All participants who were enrolled and who received at least 1 dose of study intervention within this ISA.
Modified FAS	All participants who were enrolled and who received at least 1 dose of study intervention excluding those participants who, because of COVID-19 or similar pandemics related reasons, withdrew prematurely from the study prior to Week 24 (end of study intervention [EOSI]), or had no efficacy assessment for the primary endpoint. COVID-19 or similar pandemics related reasons may include for example missed visits due to travel restriction, shortage of lab kits at the planned visit, missed collection of blood sample at key time points for the primary efficacy endpoint, etc.
IFN-FAS	All participants who were enrolled and who received at least 1 dose of PegIFN- α 2a within this ISA.
Modified IFN-FAS	All participants who were enrolled and who received at least 1 dose of PegIFN- α 2a excluding those participants who, because of COVID-19 or similar pandemics related reasons, withdrew prematurely from the study prior to Week 24 (EOSI), or had no efficacy assessment for the primary endpoint. COVID-19 or similar pandemics related reasons may include for example missed visits due to travel restriction, shortage of lab kits at the planned visit, missed collection of blood sample at key time points for the primary efficacy endpoint, etc.
Safety	All participants who received at least 1 dose of study intervention. Participants will be analyzed according to the study intervention they actually received.

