5.4.1.1.16. Flares

The criteria based on blood markers/lab tests for each of the flare types are defined as below.

1. Virologic flare is defined as follows:

Virologic flare will be assessed only for those participants who are off-treatment and had HBV DNA $< \text{LLOQ}$ at the last observed point on all study treatments.

The start of a confirmed virologic flare is defined as the first date of two consecutive visits with HBV DNA >200 IU/mL. The end date of the same confirmed virologic flare is defined as the first date when HBV DNA value returns to ≤ 200 IU/mL or the date of NA treatment restart, whichever comes first. Each virologic flare will be categorized based on the confirmed (i.e. two consecutive values) peak HBV DNA above any of the three thresholds within the start and end date of that flare as follows: 20,000 IU/mL, 2,000 IU/mL and 200 IU/mL.

- 1 (Yes) = confirmed** HBV DNA $>$ peak threshold.
- 0 (No) = at least one off-treatment HBV DNA measurement available and not meeting the criteria of confirmed HBV DNA $>$ peak threshold.
- 2 (Not applicable) = no off-treatment HBV DNA quantitative measurements available.

2. Off-treatment Biochemical flare is defined as follows:

The start date of a confirmed off-treatment biochemical flare is defined as the first date of two consecutive visits with ALT and/or AST $\geq 3x$ ULN and $\geq 3x$ nadir (i.e. lowest value observed up to the start of the flare) while the participant does not receive any of the study interventions. The end date of the same off-treatment biochemical flare is defined as the first date when there is a 50% reduction from the peak ALT and/or AST level & $< 3x$ ULN.

- 1 (Yes) = confirmed** ALT and/or AST $\geq 3x$ ULN and $\geq 3x$ nadir (i.e. lowest value observed up to the start of flare)
- 0 (No) = otherwise

3. On-treatment Biochemical flare is defined as follows:

The start date of a confirmed on-treatment biochemical flare is defined as the first date of two consecutive visits with ALT and/or AST $\geq 3x$ ULN and $\geq 3x$ nadir (i.e. lowest value observed up to the start of the flare) while the participant receives any of the study interventions. The end date of the same on-treatment biochemical flare is defined as the first date when there is a 50% reduction from the peak ALT and/or AST level & $< 3x$ ULN, regardless of stopping the study interventions.

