5.4.1.3.7. Time to First Flare

Time to first biochemical flare (on- and off-treatment), clinical flare off-treatment, and virologic flare off-treatment will be evaluated.

Time to first on-treatment flare will be defined as the number of days between the date of first study intervention intake and the date of the first occurrence of on-treatment flare (i.e. the date of the first on-treatment flare [the first of the two confirmation visits] of each type- the date of first study intervention intake+1). The participants who withdrew early from the study before experiencing on-treatment flare or who did not experience on-treatment flare will be censored at the last available blood markers or liver enzymes assessment at or before EOT.

Time to the first off-treatment flare will be defined as the number of days between the date of last study intervention intake and the date of the first occurrence of off-treatment flare (i.e. the date of experiencing the first off-treatment flare [the first of the two confirmation visits] of each type- the date of last study intervention intake). The participants who withdrew early from the study before experiencing off-treatment flare or who did not experience off-treatment flare will be censored at the last available blood markers or liver enzymes assessment.

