5.4.2. Analysis Methods

All secondary endpoints will be analyzed using the FAS. The analysis may be repeated in the IFN-FAS and modified FAS/IFN-FAS analysis sets if there is a difference of at least 2 participants between analysis sets.

Some analysis will be performed by group, as defined in Section 5.1.10. Summaries and graphs will be provided for each analysis phase, unless specified otherwise.

All secondary endpoints will be analyzed based on the observed case data. Additional analyses with specific imputation methods for missing data are added for selected endpoints.

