5.4.2.1.2. NA Treatment Completion Criteria at Week 24 and During FU

The count and proportion of participants (and associated 90% CI) who met the NA treatment completion criteria at the end of treatment period 2, will be summarized.

Starting at end of treatment period 2, the incidence of participants who did not meet the NA treatment completion criteria will be summarized at each timepoint during the study, accompanied by the distribution of each of the 4 criteria that is not met. The NA treatment completion criteria are based on a threshold for the laboratory tests of ALT, HBV DNA, HBeAg and HBsAg.

The count and proportion of participants (and associated 90% confidence interval) who met the NA treatment completion criteria (Section 5.4.1.1.1) at any time during the FU phase will be summarized. All the NA treatment completion criteria will be checked based on clinical laboratory tests in FU phase.

5.4.2.1.2.1. NA Re-Treatment Criteria During FU

The count and proportion of participants (and associated 90% CI) who meet the criteria for NA re-treatment at any time during FU will be summarized descriptively. In addition, the count and proportion of participants (and associated 90% CI) who met the criteria according to the flag on the CRF page of 'NA Re-treatment Criteria Assessment' during the follow-up phase will be summarized over time.

The count and proportion of participants (and associated 90% CI) who re-started NA treatment during the follow-up phase on the basis of the ‘Study Drug Administration for NA’ CRF page will be summarized separately over time.

A cross-tabulation of participants who actually re-started NA treatment (re-started/not restarted) versus participants who met the above criteria (met/not met) will be presented over time.

5.4.2.1.2.2. HBsAg Cut-offs

The cut-offs for HBsAg values, decreases from baseline and RT will be used in separate summaries over time. The count and proportion of participants who meet those HBsAg thresholds during the study will be summarized descriptively by analysis phase over time and displayed in graphs like bar charts.

Cross-tabulations overtime of quantitative HBsAg (<LLOQ, ≥LLOQ) versus qualitative HBsAg (positive, negative), respectively, will also be presented.

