5.5.1.4. Endpoints for Correlation

5.5.1.4.1. Association Between Baseline Characteristics/Viral Blood Markers and Selected Efficacy Variables

Correlations between baseline characteristics and on-treatment HBV blood markers with off-treatment endpoints will be evaluated. The list of HBV blood markers, including but not limited to, are defined in [Table 6](#).

A categorical off-treatment HBV marker will be evaluated if there is at least 10% response.

Table 6: Pairs of off treatment endpoints and baseline characteristics/on treatment HBV markers

Off treatment HBV marker	Baseline Characteristics/On treatment HBV marker
HBsAg change from baseline at FU Week 24	
 • Age • HBsAg value at baseline • HBsAg change from baseline at Week 12 • HBsAg change from baseline at Week 24 • NA treatment completion at Week 24 (Yes; No) • Treatment failure (Yes; No)
HBsAg change from baseline at FU Week 48	
 • Age • HBsAg value at baseline • HBsAg change from baseline at Week 12 • HBsAg change from baseline at Week 24 • NA treatment completion at Week 24 (Yes; No) • Treatment failure (Yes; No)
HBsAg seroclearance at FU Week 24 (Yes; No)	
 • Age • HBsAg value at baseline • HBsAg change from baseline at Week 12 • HBsAg change from baseline at Week 24 • NA treatment completion at Week 24 (Yes; No) • Treatment failure (Yes; No)
HBsAg seroclearance at FU Week 48 (Yes; No)	
 • Age • HBsAg value at baseline • HBsAg change from baseline at Week 12 • HBsAg change from baseline at Week 24 • NA treatment completion at Week 24 (Yes; No) • Treatment failure (Yes; No)
NA re-treatment at FU Week 24 (Yes; No)	
 • Age • HBsAg value at baseline • HBsAg change from baseline at Week 12 • HBsAg change from baseline at Week 24 • Treatment failure (Yes; No)
NA re-treatment at FU Week 48 (Yes; No)	
 • Age • HBsAg value at baseline • HBsAg change from baseline at Week 12 • HBsAg change from baseline at Week 24 • Treatment failure (Yes; No)
Partial cure at FU Week 24 (Yes; No)	
 • Age • HBsAg value at baseline

Table 6: Pairs of off treatment endpoints and baseline characteristics/on treatment HBV markers

Off treatment HBV marker	Baseline Characteristics/On treatment HBV marker

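### Off-treatment biochemical flare and NA re-treatment have no at-risk denominator, so participants who never stop NA count as event-free; the time-to-flare origin also fails for anyone who restarts NA

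*SAP*

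**What the plan says.** **Denominator.** SAP 5.4.2.1.15 (Flares) says: "The incidence rate will be calculated and summarized for each type of on-treatment or off-treatment flares (virologic, biochemical and clinical) separately". It does not say out of whom. The general rule in SAP 5.4.2 is: "All secondary endpoints will be analyzed using the FAS". SAP Section 4 defines the FAS as "All participants who were enrolled and who received at least 1 dose of study intervention within this ISA", and SAP 1.2 gives its planned size: "Approximately 50 virologically suppressed CHB-infected participants, 18-65 years (inclusive) of age, will be enrolled in this study".

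**Who can have the event.** Under Protocol 4.1 and 6.6, participants who meet the NA completion criteria at Week 24 stop NA at FU Week 2, and the others stay on NA for the whole follow-up. Protocol 6.6 also lets some participants stop NA after early discontinuation, in consultation with the sponsor. SAP 5.4.1.1.16 defines off-treatment as the time after every study intervention, NA included, has been stopped.

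**Coding (SAP 5.4.1.1.16).** Virologic flare is assessed only in off-treatment participants and has a third code: "2 (Not applicable) = no off-treatment HBV DNA quantitative measurements available". Off-treatment biochemical flare and clinical flare have only codes 1 and 0, with 0 for everyone not meeting the definition. The section also says that clinical flares are assessed only off-treatment.

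**NA re-treatment (SAP 5.4.2.1.2.1).** The plan gives the count and proportion of participants "who meet the criteria for NA re-treatment at any time during FU will be summarized descriptively", and a separate proportion who actually restarted. Neither is limited to participants who had stopped NA. SAP Table 6 correlates NA re-treatment (one row begins "NA re-treatment at FU Week 24 (Yes; No") with HBsAg change and treatment failure, again without a restriction.

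**Time to first off-treatment flare (SAP 5.4.1.3.7).** This is "the number of days between the date of last study intervention intake and the date of the first occurrence of off-treatment flare". Participants without a flare are censored at their last assessment, and NA restart is not mentioned. SAP 5.1.11 ends the off-treatment period when NA re-treatment starts.

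**The concern.** Flare frequency and NA re-treatment are listed secondary endpoints. The clinical question behind them is the risk to a participant who comes off all treatment. Protocol 4.2 reports a severe flare after NA discontinuation in another study, which led to closer monitoring and revised re-treatment criteria here. A proportion over everyone dosed does not answer that question, because it mixes the risk after stopping with the fraction who stopped.

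The SAP handles the same problem elsewhere. It restricts virologic flare as above, adds summaries limited to participants off all interventions for HBsAg seroclearance (5.4.2.1.3.2) and HBV DNA below LLOQ (5.4.2.1.10), and assesses only such participants in 5.4.2.1.11. Off-treatment biochemical flare and NA re-treatment have no equivalent. The flare types listed together in 5.4.2.1.15 could therefore be reported on different denominators.

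The time-to-event rule has its own defect. Study intervention includes NA (SAP 5.1), so a participant who flares and restarts NA has a literal last intake after the flare.

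**Working it through.** **1. The plan's own figures.** The documents give no flare or re-treatment rate. Their only precision figures are the two-sided 90% Clopper-Pearson intervals in SAP Table 1. With limits from beta quantiles at alpha = 0.10, 25/50 gives 0.376 to 0.624 (width 0.248) and 10/20 gives 0.302 to 0.698 (width 0.396). All eight intervals in that table reproduce to three decimals, so the same method is used below.

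**2. Dilution.** Let x participants have the event and m stop all interventions. All x are among the m.
- FAS proportion = x/50. At-risk proportion = x/m.
- At-risk proportion / FAS proportion = 50/m.
- m = 10 gives 5; m = 20 gives 2.5; m = 30 gives 1.67; m = 40 gives 1.25.

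To show the effect on a reported result, assume a 40% risk among stoppers. Both m and the 40% are assumptions.

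| m | x | FAS, x/50 (90% CI) | At risk, x/m (90% CI) |
|---|---|---|---|
| 10 | 4 | 8.0% (2.8-17.4) | 40.0% (15.0-69.6) |
| 20 | 8 | 16.0% (8.2-27.0) | 40.0% (21.7-60.6) |
| 30 | 12 | 24.0% (14.5-36.0) | 40.0% (25.0-56.6) |
| 40 | 16 | 32.0% (21.2-44.5) | 40.0% (26.9-54.2) |

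The same risk is reported as anything from 8% to 32%, depending only on how many stopped. For m = 10, 20 and 30 the FAS interval excludes 40%.

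**3. Time origin.** Use the target days in SAP Table 4b. NA is stopped at FU Week 2 (day 15), the flare is at FU Week 12 (day 85), and NA is then restarted and taken to FU Week 48 (day 337). SAP 5.4.1.3.7 subtracts the date of last intake from the flare date.
- From the first complete stop: 85 - 15 = 70 days.
- From the literal last intake: 85 - 337 = -252 days.
- If NA is never restarted, the last intake is the stop, and the rule gives the correct 70 days.

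**4. Censoring.** SAP 5.4.1.3.1 to 5.4.1.3.5 provide for censoring at NA re-treatment for seroclearance, seroconversion and HBV DNA below LLOQ. SAP 5.4.1.3.7 does not. A participant who restarts NA without a flare therefore stays in the off-treatment risk set after the off-treatment period has ended under 5.1.11.

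**5. Table 6.** Entry requires HBsAg above 100 IU/mL at screening (Protocol 5.1, A13.1), and NA completion requires HBsAg below 10 IU/mL. Stopping under the criteria thus implies a fall from screening of more than log10(100/10) = 1 log10, so eligibility for re-treatment is linked to HBsAg response. Table 6 also evaluates a categorical off-treatment marker only with at least 10% response. In the first row of the table above, 4/50 = 8% would drop the re-treatment row, while 4/10 = 40% would keep it.

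**The case against.** - **The FAS is inferred.** SAP 5.4.2.1.15 names no set and does not define incidence rate. If a person-time rate were meant, never-stoppers would contribute no off-treatment time and nothing would be diluted. The ambiguity is real. But the outcome is coded yes/no per participant, the section speaks of participants with at least one flare, and no person-time denominator appears, so a proportion is the natural reading.
- **The observed-case rule may restrict re-treatment already.** Secondary endpoints use observed cases, and the schedule marks the re-treatment assessment as applicable only to some. If its CRF page is blank for never-stoppers, they might drop out. The SAP does not say so, and the restart proportion comes from the NA dosing page, on which never-stoppers have data.
- **The information can be pieced together.** Counts, the proportion meeting completion criteria and a restart cross-tabulation are planned, and an independent panel monitors ALT flares. This partly stands. However, meeting the criteria is not the same as stopping, and no interval for the at-risk proportion would be reported.
- **Clinical flare is assessed only off-treatment and needs a virologic flare.** This stands, so for clinical flare only the missing code is at issue.
- **Censoring at NA restart may be informative,** because rises in HBV DNA and ALT trigger restart. This stands as a limitation to report. It does not justify keeping re-treated participants in an off-treatment risk set.
- **The study is exploratory and descriptive.** This stands: no hypothesis test and no primary-endpoint result is affected.

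**Conclusion.** The point holds for off-treatment biochemical flare and for NA re-treatment. Followed as written, the plan counts participants who never stop NA as event-free and shrinks both proportions to m/50 of the at-risk value. That rests on reading the FAS default into sections that name no denominator, on N = 50, and on an m that the documents do not give. The factors of 5 to 1.25 are a range for m = 10 to 40, not an estimate. The time origin is under-specified and fails for participants who restart NA.

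Four stronger conclusions that a reader might draw are not supported:
- That every off-treatment flare rate uses the FAS. Virologic flare is restricted to off-treatment participants.
- That the time origin is wrong throughout. It works for anyone who stops and does not restart.
- That Table 6 must show a positive association between re-treatment and the 2 log10 response. Stopping guarantees only a fall of more than 1 log10. A participant going from 500 to 9 IU/mL falls by log10(500/9) = 1.74, stops NA, and is still a treatment failure under SAP 5.4.1.1.6. The link is with HBsAg response in general, and its strength is unknown.
- That post-withdrawal flares were the sole reason for Protocol Amendment 3. The removal of JNJ-6379 was also a primary reason.

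**What to change.** In the SAP:
1. Add a flag, taken from dosing records, for participants who stopped all study interventions including NA. Basing it on actual stopping also captures early discontinuers who stopped NA.
2. Code participants without the flag as Not applicable for off-treatment biochemical flare, clinical flare and NA re-treatment.
3. Report these proportions among flagged participants, with the FAS shown second, and state that incidence rate means a proportion of participants.
4. Restrict the Table 6 NA re-treatment rows, and their 10% threshold, to the same set.
5. In 5.4.1.3.7, start the clock at the last intake before the first complete stop of all interventions, and censor at NA restart, consistent with 5.1.11. Make the last-dose wording in 5.1.11 refer to the same stop, and note that this censoring may be informative.

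The cost is SAP wording and one derived flag, with no change to study conduct or data collection. The reported proportions will be less favourable and their intervals wider.
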